2.3 Risk/Benefit Assessment

2.3.1 Known Potential Risks

Valacyclovir is the prodrug of acyclovir and is a marketed antiviral medication with a well-established safety profile. In young infants, the primary toxicities of parenteral acyclovir are: 1) neutropenia, which is reversible with cessation of the drug; and 2) creatinine elevation from crystal formation in the collecting tubules of the kidneys (7). Neither of these complications have been seen in studies of oral valacyclovir in infants and children one month of age and older (8). In order to minimize the likelihood of neutropenia or elevated creatinine in the study population, the starting valacyclovir dose regimen in this study will be 10 mg/kg/dose administered two times per day, which is one-third of the FDA-approved dose for children 2 years of age and older of 20 mg/kg/dose administered three times per day. Each subject will be carefully monitored for bone marrow toxicity (e.g., neutropenia) and nephrotoxicity (e.g., elevated creatinine) and the drug will be stopped if significant toxicities are encountered in a given subject.

There are no alternative therapies used in neonates potentially exposed to HSV at delivery (because they are born to women with a history of genital HSV and therefore who could be shedding virus in their genital tract) but without known exposure (no active maternal lesions at delivery). Standard of care at the current time in these potential exposures is simply to follow the baby clinically to see if they develop disease. Therefore, participating in this study will not deprive the subjects of any established therapy.

Risks to Privacy: Subjects will be asked to provide personal health information (PHI). All attempts will be made to keep this PHI confidential within the limits of the law. However, there is a chance that unauthorized persons will see the subject's PHI. All study records will be kept in a locked file cabinet or maintained in a locked room at each participating clinical site. Electronic files will be password protected. Only people who are involved in the conduct, oversight, monitoring, or auditing of this trial will be allowed access to the PHI that is collected. Any publications from this trial will not use information that will identify subjects by name. Organizations that may inspect and/or copy research records maintained at the participating site for quality assurance and data analysis include groups such as the IRB, NIAID, and the FDA.

2.3.2 Known Potential Benefits

There may be no direct benefit from the experimental treatment to the neonates potentially exposed to HSV at the time of delivery. This trial will determine what dose of oral valacyclovir provides the desired acyclovir systemic concentrations to effectively prevent infection from developing following an exposure to the virus at birth. Subjects who participate will contribute to the knowledge about the safety and pharmacokinetics of valacyclovir in neonates. We have selected the study population for this Phase 1 study carefully and deliberately, to include only those neonates whose mothers have a history of genital HSV and are on oral antiviral suppressive therapy for the last several weeks of pregnancy, as is recommended by the American College of Obstetricians and Gynecologists (ACOG) (9). However, women with a history of genital HSV infection may still shed HSV asymptomatically at delivery even when receiving antiviral suppression (25-28, 38). Babies born to these women can develop neonatal HSV disease (29), which documents that they remain at risk of acquiring neonatal HSV even when the mothers do not have active lesions at delivery. By requiring that subjects enrolled on this study be delivered to women on oral antiviral suppressive therapy, we have deliberately selected a population that could potentially benefit from participation on the study if they are exposed to HSV at delivery and if the oral valacyclovir study drug that they will receive in the study provides benefit in preventing that exposure from progressing to neonatal infection and disease.

2.3.3 Assessment of Potential Risks and Benefits

Participation in this study will not adversely increase the risk that newborns face when exposed to HSV at the time of delivery without treatment. This study will lead to the knowledge that can be used to determine the correct dosage of valacyclovir that is needed to effectively preemptively treat HSV-exposed neonates at the time of delivery. Known exposure to HSV at delivery is an exclusion criterion for study enrollment.

3. OBJECTIVES AND ENDPOINTS

Table 2. Objectives and Endpoints

OBJECTIVES	ENDPOINTS (OUTCOME MEASURES)
Primary	

 To establish the dose of valacyclovir in neonates that reliably achieves systemic acyclovir exposures comparable to 10 mg/kg of parenterally administered acyclovir 	
 Neonatal plasma acyclovir mean AUC₁₂ concentrations between 24,000 ngxhr/mL and 48,000 ngxhr/mL
Secondary	

 To define the pharmacokinetic profile of acyclovir in neonates receiving oral valacyclovir 	
 Plasma acyclovir PK parameters including maximum serum concentration (C_{max}), time to the maximum concentration (T_{max}), half-life (t_{1/2}), oral clearance (CL/F), and volume of distribution (V/F)

 To assess and describe the safety profile of valacyclovir among treated neonates 	
 Grade 3 Adverse Events (AEs) Grade 4 Adverse Events and Serious Adverse Events

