4. STUDY DESIGN

4.1 Overall Design

This is a Phase 1, open label multicenter trial to assess the safety and pharmacokinetics of oral valacyclovir in neonates who are at risk of acquiring neonatal herpes simplex virus disease. This study will determine the valacyclovir dose that results in a systemic acyclovir exposure comparable to 10 mg/kg of parenterally administered acyclovir, which is an AUC₀₋₁₂ of 24,000 ngxhr/mL to 48,000 ngxhr/mL. Neonates whose mothers have a history of genital HSV infection and are receiving oral valacyclovir in the last several weeks of pregnancy, as per the recommendations of the American College of Obstetrics and Gynecology (ACOG) (9), will be eligible for enrollment. The mothers can have no visible evidence of HSV lesions at the time of delivery, and the neonates will have no signs or symptoms of neonatal HSV disease. Neonates born to women with active herpetic lesions will be excluded from the study because their management is determined by the American Academy of Pediatrics algorithm published in 2013 (10) and in the 2015, 2018, and 2021 Red Books (6, 11, 12). Likewise, any baby with signs or symptoms suggestive of neonatal HSV disease will be excluded from this study and instead managed per standard of care.

The starting dose regimen of oral valacyclovir assessed will be 10 mg/kg administered two times daily for 5 days (**Cohort 1**). This dosage has been studied in patients 1 year through 11 years of age, who received twice-daily dosing for 3-5 days, while a single dose of 25 mg/kg has been studied down to 1 month of age (8). Cohort 1 will be comprised of eight subjects. Following

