6.1.3 Dose Escalation

Dose selection for Cohort 2 will be predicated upon the pharmacokinetic data from Cohort 1. Specifically, the target range of acyclovir exposure is between 24,000 ngxh/mL and 48,000 ngxh/mL. If the mean of observed acyclovir exposures of subjects in Cohort 1 are below 24,000 ngxh/mL, AND if no Grade 3 or Grade 4 AEs or SAEs are detected in any of the study subjects, then the 8 subjects enrolled in Cohort 2 will receive oral valacyclovir at a dose of 20 mg/kg administered two times daily for 5 days. Alternatively, if the mean of observed acyclovir exposures of subjects in Cohort 1 are above 48,000 ngxh/mL AND if no Grade 3 or Grade 4 AEs or SAEs are detected in any of the study subjects, then the 8 subjects enrolled in Cohort 2 will receive oral valacyclovir at a dose that has been linearly adjusted downward to target 36,000 ngxh/mL area-under-the-concentration-time curve from 0 to 12 hours (AUC₁₂). If the mean of observed acyclovir exposures of subjects in Cohort 1 are within the target range of 24,000 ngxh/mL to 48,000 ngxh/mL, Cohort 2 will not be opened for enrollment unless suggested by the Safety Monitoring Committee (SMC) (see [Section 9.4.6](#)).

If the targeted exposure is not achieved in Cohorts 1 and 2 and the safety data are acceptable, it is possible, but not anticipated, that additional dosing cohorts could be recommended based upon the results of subjects in the first two cohorts. If such a recommendation is made, dose selection and subject enrollment and assessment will follow the approach used for Cohort 2.

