9.2 Sample Size Determination

The sample size will be characterized by the width of a 95% confidence interval for AUC_{∞} in Cohort 1. As previously noted, in infants 1-2 months of age, the mean (\pm SD) AUC_{∞} is 36,000 (\pm 12,000) ngxh/mL for a normalized dose of 10 mg/kg of IV acyclovir (8). A higher (lower) dose for Cohort 2 will be considered when observed acyclovir exposures in Cohort 1 are below the mean of 24,000 (above 48,000) ngxh/mL. Assuming a constant coefficient of variation of 0.3333 in determining the standard deviation of AUC_{∞} for a given mean, a sample size of 8 will be characterized in terms of the width of a 95% two-sided confidence interval for the mean. If the observed mean is 24,000 ngxh/mL and using a standard deviation of 8,000 ngxh/mL, a two-sided 95% confidence for the mean AUC_{∞} is (17,312-30,688), i.e. the true mean can be as low as 17,312 ngxh/mL but no higher than 30,688 ngxh/mL. If the observed mean is 48,000 ngxh/mL and using a standard deviation of 15,998 ngxh/mL, a two-sided 95% confidence interval for the mean AUC_{∞} is (34,625-61,375), i.e., the true mean can be as high as 61,375 ngxh/mL but no lower than 34,625 ngxh/mL. For the confidence intervals for other sample sizes, please see table below.

For the 95% upper bound for the proportion experiencing AEs or SAEs when 0 are observed in a sample size of n. For example, if n=8 and no SAEs are observed, then there is 95% confidence that the rate is no more than 36.9%. If n=10, there is 95% confidence that the rate is not more than 30.8%. The larger the n, the tighter (i.e., closer to 0) the upper bound.

Table 5. Sample Size Determination

N	95% Confidence Bound for Event Rates*	95% CI for Mean AUC _∞ assuming a sample mean of 24,000 and SD=8,000		95% CI for Mean AUC _∞ assuming a sample mean of 48,000 and SD=15,998	
		Lower	Upper	Lower	Upper
5	0.5218	14,066.69	33,933.31	28,135.86	67,864.14
6	0.4593	15,604.52	32,395.49	31,211.13	64,788.87
7	0.4096	16,601.23	31,398.77	33,204.32	62,795.68
8	0.3694	17,311.83	30,688.17	34,625.34	61,374.66
9	0.3363	17,850.66	30,149.34	35,702.85	60,297.15
10	0.3085	18,277.15	29,722.86	36,555.72	59,444.28
11	0.2849	18,625.53	29,374.47	37,252.40	58,747.60
12	0.2646	18,917.04	29,082.96	37,835.36	58,164.64
13	0.2471	19,165.65	28,834.35	38,332.51	57,667.49
14	0.2316	19,380.94	28,619.06	38,763.03	57,236.97
15	0.2180	19,569.75	28,430.25	39,140.60	56,859.40

*when no events are observed

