9.4 Statistical Analyses

The primary objective of this study is to describe the acyclovir AUC₁₂ following oral dosing of valacyclovir at the proposed starting dose in Cohort 1 and a linearly adjusted dose in Cohort 2 if required to achieve the targeted exposure. As such, only descriptive statistics will be needed to summarize the pharmacokinetic data. This is an observational pharmacokinetic study with no comparator arms. Our goal is to generate preliminary pharmacokinetic data in this population to help inform larger dosing/efficacy trials in the future. The AUC₁₂ will be the primary parameter summarized, but secondary objective pharmacokinetic parameters such as CL/F, T_{1/2}, C_{max}, V/F, and others will also be summarized using descriptive statistics. These statistics will include at least the mean, standard deviation, coefficient of variation, median, range, and mean.

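### The primary endpoint looks only at whether the mean AUC₁₂ of eight infants lies in 24,000–48,000, which cannot by itself support the word *reliably* in the objective

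*Protocol*

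**What the plan says.** - **Objective** (Protocol section 3, Table 2; also the synopsis and SAP 3.1): "To establish the dose of valacyclovir in neonates that reliably achieves systemic acyclovir exposures comparable to 10 mg/kg of parenterally administered acyclovir".
- **Endpoint** (same table; SAP 3.2): "Neonatal plasma acyclovir mean AUC₁₂ concentrations between 24,000 ngxhr/mL and 48,000 ngxhr/mL".
- **Cohort rule** (Protocol 6.1.3, with the same limits in 4.1 and 9.4.6 and in SAP 4.4.5 and 6.6): the point estimate is compared with the two limits. One branch begins "If the mean of observed acyclovir exposures of subjects in Cohort 1 are within the target range of 24,000 ngxh/mL to 48,000 ngxh/mL", and in that case Cohort 2 stays closed unless the SMC suggests otherwise. Section 9.4.6 adds that the SMC may suggest another Cohort 2 dose when the Cohort 1 mean is in range but near a limit. The SAP records that Cohort 2 was opened after SMC review.
- **Cohort size** (Protocol 4.1): "Cohort 1 will be comprised of eight subjects". Section 9.2 describes this size by the width of a two-sided 95% CI for mean AUC∞: "Assuming a constant coefficient of variation of 0.3333 in determining the standard deviation of" AUC∞. That CV is 12,000/36,000, from IV acyclovir in infants 1–2 months old.
- **PK analysis** (Protocol 9.4): descriptive only. "These statistics will include at least the mean, standard deviation, coefficient of variation, median, range, and mean". Section 9.4.2 gives the method of calculating AUC₁₂ but no interval. Section 9.4.1 has a general line on a confidence level of at least 95%, and 9.4.8 provides for individual listings.
- **SAP** (sections 1 and 10): all PK analysis is deferred to a separate PK analysis plan, which was not among the documents reviewed.

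**The concern.** *Reliably* is a statement about how consistently infants reach the exposure. A cohort mean inside a range does not measure that: a few high values can carry the mean over 24,000 while many infants lie below it. No minimum in-range share is stated anywhere, and no confidence limit has to be met.

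The precision argument is also not carried through. Section 9.2 justifies eight infants by the width of an interval, but for a different quantity (AUC∞ after IV dosing) from the one analysed (AUC₁₂ after oral dosing in newborns). Sections 9.4 and 9.4.2 then name no interval for AUC₁₂.

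At stake is what the final report may claim. Section 9.4 says the results are meant to inform larger dosing and efficacy trials. A report could state that a dose reliably achieves the target when the analysis has shown only that one mean of eight fell in a wide range.

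**Working it through.** **Inputs.** n = 8 (Protocol 4.1); CV = 1/3 (9.2); limits 24,000 and 48,000 (section 3). The documents give no distribution, so normal and log-normal are both used, as assumptions.

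**1. The plan's own figures.** Mean ± t(0.975, 7) × SD/√8, with t = 2.3646 and t/√8 = 0.8360.
- SD 8,000: 24,000 ± 6,688 = 17,312 to 30,688.
- SD 15,998: 48,000 ± 13,375 = 34,625 to 61,375.

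Both match section 9.2. The AUC columns of Table 5 reproduce for every n from 5 to 15, to within 0.01.

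**2. Share of infants below 24,000 at true mean m.**
- Normal: Φ((24,000 − m)/(m/3)). At m = 26,000: Φ(−2,000/8,667) = Φ(−0.231) = 41%.
- Log-normal: σ² = ln(1 + 1/9) = 0.1054, σ = 0.3246, μ = ln m − σ²/2. At m = 26,000: Φ((ln(24/26) + 0.0527)/0.3246) = Φ(−0.084) = 47%.

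**3. Probability that the mean of eight is in range.** Normal: standard error m/(3√8). At m = 26,000 this is 3,064, and 1 − Φ(−2,000/3,064) = 74%; the upper limit is irrelevant here. Log-normal: 400,000 simulated cohorts.

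**4. Probability that the mean is in range and at least 4 of 8 infants are below 24,000.** Simulated under both shapes.

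| True mean | Infants below 24,000, % (normal / log-normal) | Endpoint met, % | Endpoint met with ≥4 of 8 below, % |
|---|---|---|---|
| 22,000 | 61 / 67 | 22 / 21 | 10 / 14 |
| 24,000 | 50 / 56 | 50 / 48 | 18 / 26 |
| 26,000 | 41 / 47 | 74 / 73 | 20 / 31 |
| 28,000 | 33 / 38 | 89 / 90 | 16 / 25 |
| 33,000 | 21 / 21 | 99.0 / 99.6 | 5 / 6 |
| 36,000 | 16 / 14 | 99.5 / 99.3 | 2 / 2 |

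**5. Sensitivity to the CV (assumed 0.2 to 0.6).** At a true mean of 24,000 the share below is 50% throughout (normal) and 54% to 61% (log-normal). At 36,000 it runs from 5% to 29% (normal) and from 3% to 32% (log-normal).

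**6. Precision for oral AUC₁₂.** The CI half-width as a fraction of the mean is 0.836 × CV: 28% at CV 0.333. The IV figure contains no absorption variability. Adding an independent 30% CV for bioavailability, which is an assumption, gives √(0.333² + 0.30²) ≈ 0.45 and a half-width of 38%. Across CVs of 0.2 to 0.6 the half-width runs from 17% to 50%.

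**7. The benchmark for an in-range share.** The range is the IV reference mean ± 1 SD (36,000 ± 12,000, Protocol 4.1), so under normality Φ(1) − Φ(−1) = 68% of that reference population lies inside it.

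**8. What eight infants can show.** Clopper-Pearson 95% lower limits for the in-range share are 63% for 8/8 (0.025^(1/8) = 0.631), 47% for 7/8 and 35% for 6/8.

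**The case against.** The case for leaving the plan alone has real substance.

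- **A reader might infer that no interval is planned at all.** The documents do not support that. The list in 9.4 is a stated minimum, 9.4.1 has a general 95% line for estimation, 9.2 uses an interval for mean AUC∞, and the PK analysis plan was not supplied. What stands is narrower: the protocol and SAP name no AUC₁₂ interval and no in-range share, and neither enters the decision.
- **A reader might infer that any dose meeting the endpoint leaves half the infants too low.** That holds only near the lower limit. At 33,000 about 21% are below, and at 36,000 it is 14–16%.
- **A reader might take 24,000 as a minimum for each infant, and 68–71% in range at a mean of 36,000 as failure.** The documents apply the range to the mean, and about 68% in range is what the IV reference would itself show. Matching that is what a comparable exposure means.
- **SMC discretion.** The near-limit provision in 9.4.6 does address a Cohort 1 mean close to an edge. It is unquantified, however, and concerns the choice of Cohort 2 dose, not the endpoint or the final wording.
- **Little information is lost.** With individual values listed and mean and SD reported, a reader could work out the missing figures. That is true, and it is why the change is cheap, but it leaves the report's conclusion without a stated basis.
- **The study is described as preliminary and descriptive.** This argues for softening the claim. It does not reconcile objective and endpoint.

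**Conclusion.** The concern holds as a mismatch between objective and endpoint, with a reporting gap beside it. A mean-only criterion on eight infants cannot show that a dose reaches the exposure reliably. At the plan's CV the gap is material when the true mean is near 24,000: at 26,000 the endpoint is met about three times in four, although more than two infants in five are below 24,000. It is small at the centre of the range.

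The size rests on the CV of 1/3, on the two assumed distribution shapes, and on the PK analysis plan not already containing these summaries.

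This should be fixed before the final PK analysis. It does not invalidate the design. Nor would the fix let eight infants prove reliability: even 8 of 8 in range leaves a lower limit of 63%, under the 68% benchmark. In most outcomes the supportable conclusion will be about the mean.

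**What to change.** In Protocol 9.4 and 9.4.2 and in the PK analysis plan, specify by dose:

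1. Arithmetic and geometric mean AUC₁₂, each with a 95% CI. The second, repeated *mean* in the 9.4 list can give way to the geometric mean.
2. The number and percentage of infants below 24,000, within 24,000–48,000 and above 48,000, with Clopper-Pearson 95% CIs, read against the roughly 68% expected in the IV reference population under normality.
3. A wording rule: use *reliably* only for a conclusion that the in-range share and its CI support; otherwise conclude that mean AUC₁₂ lies within the target range.
4. A sentence stating that the precision figures in 9.2 are for AUC∞ with the IV CV at 1–2 months of age, and that precision for oral AUC₁₂ may be lower (half-width 28% of the mean at CV 0.33, 38% at an assumed 0.45).

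The planning table need not be recomputed with the Cohort 1 CV: that would be after the fact and would not change n. Because Cohort 1 has already been reviewed, the report should say when these summaries were added.

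The cost is some wording and one small table, from data already collected. The downside is that the stated precision, and probably the conclusion, will look less favourable.

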4. STUDY DESIGN

4.1 Overall Design

This is a Phase 1, open label multicenter trial to assess the safety and pharmacokinetics of oral valacyclovir in neonates who are at risk of acquiring neonatal herpes simplex virus disease. This study will determine the valacyclovir dose that results in a systemic acyclovir exposure comparable to 10 mg/kg of parenterally administered acyclovir, which is an AUC₀₋₁₂ of 24,000 ngxhr/mL to 48,000 ngxhr/mL. Neonates whose mothers have a history of genital HSV infection and are receiving oral valacyclovir in the last several weeks of pregnancy, as per the recommendations of the American College of Obstetrics and Gynecology (ACOG) (9), will be eligible for enrollment. The mothers can have no visible evidence of HSV lesions at the time of delivery, and the neonates will have no signs or symptoms of neonatal HSV disease. Neonates born to women with active herpetic lesions will be excluded from the study because their management is determined by the American Academy of Pediatrics algorithm published in 2013 (10) and in the 2015, 2018, and 2021 Red Books (6, 11, 12). Likewise, any baby with signs or symptoms suggestive of neonatal HSV disease will be excluded from this study and instead managed per standard of care.

The starting dose regimen of oral valacyclovir assessed will be 10 mg/kg administered two times daily for 5 days (**Cohort 1**). This dosage has been studied in patients 1 year through 11 years of age, who received twice-daily dosing for 3-5 days, while a single dose of 25 mg/kg has been studied down to 1 month of age (8). Cohort 1 will be comprised of eight subjects. Following

informed consent, each subject will receive 10 mg/kg of oral valacyclovir, and may start taking oral valacyclovir while still in the birth hospital, with subsequent dosing at home, or may start taking oral valacyclovir following discharge from the birth hospital. **Study Day 1** is the day that the first dose of oral valacyclovir is administered. Following signing of informed consent but prior to administration of the first dose of valacyclovir, hematology and chemistry safety labs (white blood cell count and differential for absolute neutrophil count, hemoglobin, platelet count, alanine aminotransferase, and creatinine) will be obtained and values checked; if no baseline hematology or chemistry values are Grade 1 toxicity or higher then dosing of valacyclovir will proceed; if any value is Grade 1 toxicity or higher, the subject will be withdrawn from the study prior to receiving any doses of study medication. In addition, the subject must have had a first void before receiving a first dose of study medication. A single plasma sample will also be obtained for a baseline acyclovir concentration, since the mothers of enrolled subjects will have been taking antiviral medication prior to delivery. Dropouts and withdrawn subjects may be replaced to reach the target sample size of eight subjects. Subjects will return to the study site on Study Day 5 (window: Study Day 4 through Study Day 5), and also will be assessed for adverse events and concomitant medications on Study Day 10 (window: Study Day 7 through Study Day 13) and on Study Day 42 (window: Study Day 35 through Study Day 49), although the Study Day 10 and 42 assessments may occur via telephone or in-person study visits. On the Study Day 5 (window: Study Day 4 through Study Day 5) visit, plasma samples for PK assessments will be obtained around dose 7, 8, 9, or 10 of study drug at 0 hour minus 15 minutes (pre-dose), and then 1-2 hours, 4-6 hours, and 8-10 hours following administration of the valacyclovir dose (full PK profile). Safety laboratory assessments (white blood cell count with differential, hemoglobin, platelet count, alanine aminotransferase, and creatinine) will be obtained at the Study Day 1 (baseline) and Study Day 5 visits. Safety laboratory values will be classified using the Division of AIDS Toxicity Tables ([Appendix A](#)). Study drug will be stopped following the obtaining of the PK samples on Study Day 5 (window: Study Day 4 through Study Day 5). Criteria for AEs or SAEs leading to halting of the study are detailed in [Section 7.1.1](#). The total number of study days of study drug administration will be 4 or 5 (depending on where in the window the Study Day 5 visit is conducted), although the total number of doses can be 7, 8, 9, or 10 depending upon when the study drug was started on Study Day 1 and whether the PK blood draws on Study Day 5 (window: Study Day 4 through Study Day 5) are around the first or second dose that day.

The target concentration of acyclovir following oral valacyclovir dosing is 24,000 ngxh/mL to 48,000 ngxh/mL. This range was selected because a normalized dose of 10 mg/kg of parenteral acyclovir produces a mean (\pm SD) AUC_{∞} of 36,000 (\pm 12,000) ngxh/mL in infants 1-2 months of age (8). This 10 mg/kg parenteral acyclovir dose was the accepted treatment dose for **neonatal disease** in the 1980s and 1990s (14), and successfully prevents neonatal HSV SEM disease from progressing to disseminated disease (20). In the current study, antiviral therapy is being used to prevent **neonatal exposure** from progressing to **neonatal infection** (and thus to neonatal disease). The drug exposure that prevented less severe disease (SEM disease) from progressing to more severe disease (disseminated disease) has therefore been selected as the target range. Although a 20 mg/kg parenteral acyclovir treatment dose for neonatal disease improves survival in neonatal disease (2), the current study is not proposing to treat disseminated disease but rather to prevent neonatal disease from developing in the first place. Additionally, the amount of virus present on the skin and mucous membranes in exposed neonates will be lower than in 10-19 day

old infants who already have neonatal HSV disease, suggesting that lower drug exposure will be sufficient. Finally, this lower exposure has also been selected to minimize likelihood of drug toxicity.

Upon full accrual of Cohort 1, the PK and safety data will be reviewed. If the safety profile and the drug exposure concentrations in Cohort 1 are acceptable, eight new subjects will be enrolled in **Cohort 2**. The dose that these subjects will receive will be predicated upon the pharmacokinetic data from Cohort 1. If the mean of observed acyclovir exposures of subjects in Cohort 1 are below 24,000 ngxh/mL, AND if no Grade 3 or Grade 4 AEs or SAEs are detected in any of the study subjects, then the 8 subjects enrolled in Cohort 2 will receive oral valacyclovir at a dose of 20 mg/kg administered two times daily for 5 days. Alternatively, if the mean of observed acyclovir exposures of subjects in Cohort 1 are above 48,000 ngxh/mL AND if no Grade 3 or Grade 4 AEs or SAEs are detected in any of the study subjects, then the 8 subjects enrolled in Cohort 2 will receive oral valacyclovir at a dose that has been linearly adjusted downward to target 36,000 ngxh/mL area-under-the-concentration-time curve from 0 to 12 hours (AUC₁₂). The study schedule for subjects in Cohort 2 will be identical to those in Cohort 1, as described above and in the Schedule of Activities table (see [Section 1.2](#)). If the mean of observed acyclovir exposures of subjects in Cohort 1 are within the target range of 24,000 ngxh/mL to 48,000 ngxh/mL, Cohort 2 will not be opened for enrollment unless suggested by the Safety Monitoring Committee (SMC) (see [Section 9.4.6](#)).

If the targeted exposure is not achieved in Cohorts 1 and 2 and the safety data are acceptable, it is possible, but not anticipated, that additional dosing cohorts could be recommended based upon the results of subjects in the first two cohorts. If such a recommendation is made, dose selection and subject enrollment and assessment will follow the approach used for Cohort 2.

Schedule of assessments can be found in [Section 1.2, Schedule of Activities](#). Dose escalation or dose-ranging details are found in [Section 6.1.2, Dosing and Administration](#). Full details of interim analysis are found in [Section 9.4.6, Planned Interim Analysis](#)

